## 1.8. Clinical Pharmacology

[figure not shown]
Debio 1562 concentrations in plasma were obtained by using a validated enzyme-linked immunosorbent assay ligand binding assay.

Debio 1562 PK parameters from the FIH study 0301 were determined for Cycle 1 for each patient. In most cases,  $t_{max}$  coincided with the end of infusion, as expected. Overall results were fairly consistent across cycles, suggesting that the PK of Debio 1562 does not change upon repeat dosing. On average,  $C_{max}$  and  $AUC_{0-inf}$  increased with an increase in dose. Greater than proportional increases occurred at doses of 0.8 mg/kg and above when compared to the 0.1 to 0.7 mg/kg doses, most likely due to an increase in the mean clearance (CL) in the lower dose range. [REDACTED]

[REDACTED] These changes in terminal elimination rate are consistent with target mediated drug disposition at low doses, with saturation of this mechanism occurring at higher doses. [REDACTED] in each group, the values for  $V_{ss}$  were consistent with plasma volume [REDACTED]

[REDACTED] There was no apparent accumulation of Debio 1562 in repeated dosing.

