### **5.9. Debio 1562 and Rituximab Dose Modifications**

#### **5.9.1. Delay or Skip Dosing of Study Treatment**

In order for a patient to receive any study treatment (Debio 1562 alone or Debio 1562 and rituximab), the following re-treatment criteria must be met.

- ANC must be  $\geq 1.0 \times 10^9/L$  ( $1000/mm^3$ )
- Platelet count must be  $\geq 50 \times 10^9/L$  ( $50,000/mm^3$ )
- All non-hematologic toxicities must be  $\leq$  Grade 2 (except alopecia) or returned to baseline

**Cohort A and B:** If the retreatment criteria are not met on Day 1 of a given cycle, the patient should be re-evaluated within 48-72 hours, and dosing should be delayed until the criteria are met.

If the retreatment criteria are met within 14 days, study treatment should resume at planned or reduced dose (see [Section 5.9.2](#)), and the study physician may opt for the routine administration of secondary prophylaxis with G-CSF during following cycles.

If the retreatment criteria are met within 14-21 days, study treatment should resume at planned or reduced dose (see [Section 5.9.2](#)), and secondary prophylaxis with G-CSF should be administered if the delay was due to unmet hematological parameters.

If dosing is delayed for  $> 21$  days due to unmet retreatment criteria, both study treatments should be discontinued (see [Section 5.9.2](#)).

**Cohort B:** If the retreatment criteria are not met on Day 8 or Day 15 of a given cycle, dosing of Debio 1562 should be skipped on that visit, secondary prophylaxis with G-CSF will be indicated

and the retreatment criteria will be re-evaluated at the next visit when infusion is planned to occur. If the retreatment criteria are not met on Day 1 of the next cycle, the rules described above for the delay on Day 1 of any given cycle will apply.

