#### 5.9.2.2 Adverse Events Requiring Dose Reduction

Rituximab dose reductions are not allowed. If patients do not tolerate treatment with rituximab, they may continue on Debio 1562 alone.

For **Cohort A**, dose reduction of Debio 1562 will occur as follows:

- 0.7 mg/kg → 0.4 mg/kg

For **Cohort B**, dose reduction of Debio 1562 will occur as follows:

- 0.4 mg/kg → 0.2 mg/kg
- 0.2 mg/kg → 0.1 mg/kg

Dose of Debio 1562 should be reduced in patients experiencing the AEs below:

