## 10.3. Pharmacokinetic (PK) Analyses

PK parameters that will be evaluated include, but are not limited to:  $C_{max}$ ,  $T_{max}$ , Terminal half-life ( $t_{1/2}$ ),  $V_{ss}$ , CL,  $AUC_{0-t}$ ,  $AUC_{inf}$ . These will be derived from plasma concentrations of Debio 1562, total and/or naked humanized CD37 mAb (K7153A), DM1 (free and bound), as well as potential catabolites, and total rituximab, using the actual sampling times. Concentration data and all PK parameters will be listed per patient and summarized descriptively per dose. If appropriate, non-compartmental (Model independent) methods will be used to compute the PK parameters using the latest version of SAS or Phoenix WinNonlin software.

The PK disposition of Debio 1562 (and rituximab, if deemed appropriate) will also be described through a population PK approach using NONMEM (ICON Solutions). This evaluation will be reported separately.

Individual plasma concentration versus actual time profiles for each patient and treatment, as well as the mean (+/- standard deviation) plasma concentration versus scheduled time profiles for each dose level, will be presented graphically on normal and semi-log scale.

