10.5 Pharmacokinetics

Blood samples for pharmacokinetics will be collected as outlined in [Appendix D](#)(Safety run-In and Phase II), [Appendix E](#) (Cohort A, Part 2 and 3) and [Appendix F](#) (Cohort B, Part 2 and 3).

Concentration of Debio 1562, anti-drug antibody (ADA) Debio 1562, Debio 1562 total antibody (TAb), DM1 Free, DM1-SMCC-lysine, DM1-SMCC, Rituximab, and ADA Rituximab will be summarized by cohort and per visit and also by regimen. The following summary statistics will be produced: the number of non-missing values, the arithmetic mean, the standard deviation, the coefficient of variation, the median, the first and third quartiles, the minimum, the maximum, the geometric mean, the geometric standard deviation and the geometric coefficient of variation.

[figure not shown]
Concentrations that are below the limit of quantification will be handled as follows:

- All pre-dose concentrations observed before cycle 1 day 1 that are below the limit of quantification will be imputed by:

- o Zero for the computation of the mean, the standard deviation, and the coefficient of variation
- o Half the limit of quantification for the computation of the geometric mean, the geometric standard deviation, and the geometric coefficient of variation
- All concentrations observed after the first dose date that are below the limit of quantification will be imputed by half the limit of quantification.

PK parameters, including but not limited to C_{max} , T_{max} , $t_{1/2}$ and AUC, will be summarized similarly as above for Debio 1562, Debio 1562 TAb, DM1 Free, DM1-SMCC-lysine, DM1-SMCC and rituximab.

The overall PK and PK/PD analyses will be described in a separate analysis plan.

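### SAP 10.5 groups Debio 1562 PK summaries by cohort, visit and an undefined regimen rather than per dose as protocol 10.3 requires, so modified doses are pooled with planned ones

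*SAP*

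**What the plan says.** Protocol 10.3: "Concentration data and all PK parameters will be listed per patient and summarized descriptively per dose". It adds that mean "plasma concentration versus scheduled time profiles for each dose level, will be presented graphically".

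SAP 10.5: concentrations of Debio 1562, its related analytes and rituximab "will be summarized by cohort and per visit and also by regimen". PK parameters, including Cmax, Tmax, half-life and AUC, "will be summarized similarly as above for Debio 1562, Debio 1562 TAb, DM1 Free, DM1-SMCC-lysine, DM1-SMCC and rituximab". The section names no dose stratum and no dose normalisation. It has no rule for samples taken after a reduced, skipped or switched dose, and it does not say what regimen means.

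Protocol 5.9.2.2 sets the Cohort A reduction step, "0.7 mg/kg → 0.4 mg/kg", and halves each Cohort B dose (0.4 to 0.2 and 0.2 to 0.1 mg/kg). A patient may be reduced once and may not go back up. Under protocol 5.9.1, a Cohort B patient who fails the retreatment criteria on Day 8 or Day 15 has no infusion that day: "dosing of Debio 1562 should be skipped on that visit". Protocol 5.7.4.1 lets QW patients switch to Q3W, which takes the Day 1 dose from 0.4 to 0.7 mg/kg.

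SAP 11 refers only to the protocol's amendment history, so it does not record the changed grouping.

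**The concern.** Characterising the PK of Debio 1562 is a secondary objective. If different administered doses share one cell of a cohort-by-visit table, the mean reflects the dose mix as well as the drug's disposition. Because reductions are permanent, the reduced share can grow over cycles among patients still treated. A fall in mean concentration from that cause could be read as a change in clearance over time, or as an effect of anti-drug antibodies, which protocol 6.2 sets out to examine.

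The contrast between schedules is also exposed. Protocol 1.6 motivates QW dosing by a lower peak and extended exposure, and suggests that Cmax may be linked to neutropenia. Neutropenia is itself a trigger for reduction, so dose changes may be related to exposure and may differ between cohorts.

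**Working it through.** The plan gives no figure to reproduce. The check is whether cohort plus visit fixes the dose and, where it does not, how far a mean could move.

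**1. Does cohort plus visit identify the dose?**

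| Cell | Planned dose (mg/kg) | Other doses possible in the same cell |
|---|---|---|
| Cohort A, Day 1 | 0.7 | 0.4 (reduced) |
| Cohort B, Day 1 | 0.4 | 0.2 (reduced); 0.7 (switched to Q3W) |
| Cohort B, Day 8 or 15 | 0.2 | 0.1 (reduced); none (skipped) |

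It does at planned doses only.

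**2. Reductions.** Let f be the fraction of patients at a visit on the reduced dose and r the dose ratio: r = 0.4/0.7 = 0.571 in Cohort A, and 0.2/0.4 = 0.1/0.2 = 0.5 in Cohort B. Assume exposure is proportional to dose. Then:

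- change in geometric mean = r^f − 1
- change in arithmetic mean = −f(1 − r)

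The documents give no f, so a range is shown.

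| f | A geometric | A arithmetic | B geometric | B arithmetic |
|---|---|---|---|---|
| 0 | 0% | 0% | 0% | 0% |
| 0.1 | −5.4% | −4.3% | −6.7% | −5.0% |
| 0.2 | −10.6% | −8.6% | −12.9% | −10.0% |
| 0.4 | −20.1% | −17.1% | −24.2% | −20.0% |
| 0.5 | −24.4% | −21.4% | −29.3% | −25.0% |

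For example, 0.571^0.2 = 0.894 and 0.571^0.4 = 0.799; 0.5^0.2 = 0.871 and 0.5^0.4 = 0.758. Within a single dose stratum this shift is zero by construction.

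**3. Switchers.** Protocol 1.9 says three QW patients on treatment at 14 April 2020 were given permission to switch. If all three switch and m Cohort B patients contribute at a visit (m assumed), the mean Day 1 dose in the by-cohort table is [0.4(m − 3) + 0.7 × 3]/m. For m = 3, 6, 10 and 15 this is 0.70, 0.55, 0.49 and 0.46 mg/kg, or 75%, 37.5%, 22.5% and 15% above 0.4. With m = 10 and k of the seven others reduced to 0.2, the mean is (4.9 − 0.2k)/10, so at least five must be reduced before it drops below 0.4.

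**4. Skipped doses.** A skipped infusion yields no end-of-infusion sample, so that mean does not change. Later troughs do. After a skipped Day 15, the next Day 1 pre-dose sample comes 14 days after the last dose instead of 7. Assume one compartment, linear PK, half-life t in days, and only that cycle's doses. The ratio to the planned trough is

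(0.4 × 2^(−21/t) + 0.2 × 2^(−14/t)) / (0.4 × 2^(−21/t) + 0.2 × 2^(−14/t) + 0.2 × 2^(−7/t)).

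For assumed t = 3, 5 and 7 this is 0.22, 0.40 and 0.50.

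**5. Where the effect lands.** For Cohorts A and B, protocol Appendices E and F place dense Debio 1562 sampling in Cycles 1-2. Cycles 3-6 have mainly pre-dose and end-of-infusion samples. Haematologic reductions need a second occurrence, and delay-based ones need delays in two consecutive cycles (protocol 5.9.2.2). Full-profile parameters will therefore come mostly from planned doses, and later-cycle concentrations carry most of the risk. Rituximab dose reductions are not allowed, and Tmax and half-life do not scale directly with dose.

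**The case against.** The strongest defence is that the main PK work lies elsewhere. SAP 3.2 puts PK outside its scope unless later sections say otherwise, and SAP 10.5 sends the overall PK and PK/PD analyses to a separate plan. Protocol 10.3 adds per-patient listings, individual profiles on actual time and a population PK model, all of which can use real dosing histories. A per-dose table may exist in that separate plan, which is not among these documents. This limits the consequence but does not remove the point, because SAP 10.5 itself specifies analytes, grouping, statistics and handling of values below quantification, and so governs these tables.

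Second, regimen might be meant to include dose. The protocol sometimes uses the word that way, and SAP 7.5 reports the PK population against treatment actually received. Elsewhere, however, the SAP uses regimen for QW versus Q3W (10.1.2), and treatment received is not defined as dose level. The ambiguity stands and needs a definition.

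Third, protocol 10 itself calls for concentration graphs by cohort, SAP 10.2.1 plans no formal comparison between cohorts, and SAP 10.4 tabulates dose modifications and lists infusions. All of that is true. By-cohort tables are legitimate as additional output, and a careful reader could trace the dose mix.

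A reader might also infer that dose normalisation is ruled out, because protocol 1.8 says "Greater than proportional increases occurred at doses of 0.8 mg/kg and above when compared to the 0.1 to 0.7 mg/kg doses". That sentence contrasts 0.8 mg/kg and above with the lower range. Every per-infusion dose at issue here (0.1 to 0.7) lies within the lower range, so it is little evidence against normalising among them. It does not establish proportionality there either, which is why proportionality is labelled an assumption above.

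**Conclusion.** The discrepancy is real and undeclared. Protocol 10.3 requires per-dose summaries; SAP 10.5 as written can pool different administered Debio 1562 doses in one cell. The size is conditional. With 20-40% of patients reduced and dose-proportional exposure, the geometric mean of concentration, Cmax or AUC falls about 11-20% in Cohort A and 13-24% in Cohort B with unchanged PK. It does not move if nobody is reduced.

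A reader might infer that later-cycle PK must fall artificially, or that skipped doses are averaged in with full ones. The documents support neither. No reduction rate is given, switchers move the Cohort B Day 1 mean upward in the by-cohort table, and a skipped infusion affects only later samples. The point concerns Debio 1562 analytes, chiefly later-cycle concentrations and troughs, and does not extend to rituximab.

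**What to change.** In SAP 10.5:

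- Add the actual Debio 1562 dose level (mg/kg) as a by-variable within regimen and visit or time point, as protocol 10.3 requires. Use the dose just given for post-infusion samples and the preceding administered dose for pre-dose samples. Classifying a pre-dose sample by the dose about to be given would place full-dose troughs in the reduced-dose stratum at a patient's first reduced visit.
- Define regimen as the regimen actually received.
- Flag pre-dose values that follow a skipped or delayed dose, summarise them separately from planned-interval troughs, and list them with the actual time since the last dose.

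If the separate PK plan already contains the per-dose summary, cross-refer to it from SAP 10.5 and declare the changed grouping in SAP 11.

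The cost is SAP wording and one more by-variable in the Debio 1562 tables. Some dose-level cells will be small.

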10.7 Other Analyses

10.7.1.1 *Health-Related Quality of Life*

Health-related quality of life will be evaluated based on the functional assessment of cancer therapy-lymphoma (FACT-Lym). Please refer to scoring manual (www.facit.org) for instruction for computing overall score and subscale scores. Full analysis of the health-related quality of life questionnaire is beyond the scope of this document. It will be described in a separate analysis plan.

10.8 Interim Analyses

No formal interim analysis is planned for this study. However, available safety and PK data will be reviewed by the SRC during the course of study part 1 and by the IDMC during the course of part 2 and part 3 of the study (see Section 4.2).

Tumor Type	Percentage
Astrocytoma	~95%
Oligodendroglioma	~90%
Glioblastoma	~85%
Ependymoma	~10%
Meningioma	~5%
Metastasis	~1%

10.8.1.2 Stopping Rules for Safety

The IDMC will review the safety data regularly and can recommend terminating or modifying any dosing regimen or the study to guard subjects' safety. The IDMC will monitor all safety aspects with special focus on neutropenia, febrile neutropenia, hepatic damage, pneumonitis and neuropathy.

11 SUMMARY OF CHANGES TO THE PROTOCOL

Amendment history to the protocol can be found in Section 1.10 of the protocol.

13 APPENDICES

Appendix A. SCHEDULE OF EVENTS OF SAFETY RUN-IN FOR Q3W DOSING (PART 1)

Activity	Screening	Cycles 1 and 3					Cycle 2			Cycles ≥ 4	EOT ^j	30-day Follow-up ^{f, n}
		≤ 28 days prior to 1st dose	Day 1^k	Day 2	Day 3	Day 8 ± 1 day	Day 15 ± 1 day	Day 1^k	Day 8 ± 1 day	Day 15 ± 1 day		
Informed Consent	•											
Demography	•											
Confirm disease diagnosis, stage at diagnosis and current stage	•											
Medical History	•											
Review and Document Inclusion/Exclusion Criteria	•											
Confirm patient continues to satisfy I/E Criteria		C1 only										
Physical examination ^a	•	•					•			•	•	•
Vital Signs ^b	•	•			•	•	•	•	•	•	•	•
Weight	•	•				•			•	•	•	•
Height	•											
B-symptoms	•	•					•			•	•	•
ECOG performance status	•	•					•			•	•	•
Pregnancy test (urine or serum)	•	•					•			•	•	•
Hematology and Chemistry ^c	•	•	•	•	•	•	•	•	•	•	•	•

Activity	Screening	Cycles 1 and 3					Cycle 2			Cycles ≥ 4	EOT ^j	30-day Follow-up ^{f, n}
	≤ 28 days prior to 1st dose	Day 1 ^k	Day 2	Day 3	Day 8 ± 1 day	Day 15 ± 1 day	Day 1 ^k	Day 8 ± 1 day	Day 15 ± 1 day	Day 1 ^k		(30-42 Days)
Coagulation ^c	•	•					•			•	•	•
Urinalysis ^c	•	•					•			•	•	•
Viral Serology (HBsAg)	•											
Radiologic tumor assessments ^d	•		Every 6 weeks (± 1 week) from Cycle 1 Day 1 (no schedule shift due to dose delays) ^e							• ^f	• ^f	
Biopsy tumor tissue ^g	•											
Bone Marrow Assessment ^h	•		Every 6 weeks (± 1 week) from Cycle 1, Day 1 as Clinically Indicated									
ECG (12-lead) ⁱ	•	•	•					On Day 1 of Cycles 2 and 4 to coincide with PK draws (± 1 hour)			•	•
Pharmacokinetic and Immunogenicity Assessments		See Appendix D										
AE and SAE evaluation ^l	•	•	•	•	•	•	•	•	•	•	•	•
Concomitant Medication ^m	•	•	•	•	•	•	•	•	•	•	•	•
Debio 1562 Infusion		•					•			•		
Rituximab Infusion		•					•			•		

a) Directed physical examination is acceptable while on study treatment and at the 30-day safety Follow-up Visit. Complete examination is required at screening and EOT. Physical examinations may be performed up to 3 days prior to study drug administration on Day 1 of all Cycles.

b) **Debio 1562** - vital signs (blood pressure, heart rate, temperature, and respiratory rate) will be measured immediately before each administration, every 30 min ± 5 min during the infusion (if applicable), and immediately after infusion. **Rituximab** - vital signs will be measured immediately before each administration, every 60 min ± 5 min during the infusion and immediately after infusion. For all cycles, patients must remain in the clinic for safety observation for one hour following completion of their rituximab infusion.

c) Laboratory assessments may be performed up to 3 days prior to study **drug** administration **in all cycles**. All draws on Day 1 of treatment should be pre-dose. In the event of severe toxicity, repeat laboratory tests should be performed within 48 hours, and then followed at least twice weekly until re-treatment criteria are met.

Serum Chemistry- ALB, ALK-P, ALT, AST, BUN, Ca, Cl, Creatinine, Glucose, LDH, Magnesium, Phosphorus, K, Na, Total bilirubin, Total protein, Uric acid, Immunoglobulin levels (IgG, IgA, IgM).

Hematology- Hct, Hgb, Platelet count, RBC count, WBC count with differential.

Urinalysis - Appearance, specific gravity and pH, Semi-quantitative dipstick evaluation of glucose, protein, bilirubin, ketones, leukocytes and blood, Microscopic examination of sediment to be performed if urinalysis is positive for WBC, proteins or blood.

Coagulation tests: T/INR and aPTT

- d) Radiographic tumor evaluation by CT or PET-CT scan of chest, neck, abdomen and pelvis will be performed within 28 days prior to first dose of study treatment. The anatomical regions to be assessed radiographically post baseline will be determined by individual patients' extent of disease. Whenever possible, the same radiographic scan assessment used at screening (e.g., PET-CT) should be used at all subsequent radiographic evaluations.
- e) Post-baseline disease assessments will be performed every 6 weeks from Cycle 1, Day 1 and will not shift due to dose delays.
- f) Patients discontinuing Debio 1562 for reasons other than PD will have subsequent clinic visits for radiographic assessment every 12 weeks (\pm 4 weeks) from the time of their last on-study tumor assessment until PD, or starting a subsequent anti-cancer therapy. For patients who discontinue for PD, no radiographic scans will be required at the EOT visit or the follow-up visits. All patients will be followed for survival every 12 weeks (\pm 4 weeks) from the time of the 30-day safety Follow-up visit, for up to one year from the last patient's first dose (Cycle 1 Day 1). Patients will not be required to visit the clinic for survival follow-up.
- g) Patients must have available pathology-informed tumor biopsy sample representative of the current disease, [REDACTED].
- h) If applicable, a bone marrow biopsy or aspirate will be performed within 3 months prior to first dose. A repeat bone marrow biopsy or aspirate will be required for patients with bone marrow infiltration at baseline who have a CR by imaging and physical examination, and will, in case possible and deemed acceptable by the Investigator, be performed every 6 weeks as clinically indicated. In order to better understand the effect of Debio 1562 on WBCs, bone marrow biopsies/aspirates may also be requested for those patients who experience grade 4 cytopenias.
- i) The screening ECG will be performed within 14 days prior to first treatment. In Cycles 1 and 3, ECGs will be performed within three hours prior to dose, at the end of the Debio 1562 infusion (to coincide with C_{max} and PK blood draw) and 24 \pm 4 hours after infusion. An ECG will be performed on Day 1 of Cycles 2 and 4 (inclusive) to coincide with the pre-dose PK blood draw. An ECG at the 30-day Follow-up visit is not required unless clinically indicated or if the EOT assessment was missed.
- j) EOT visit should occur within 7 days of the decision to discontinue study treatment.
- k) Cycle 1 Day 1 assessments (ECOG, weight, B Symptoms and pregnancy test) do not need to be repeated if they are collected within 3 days of study drug administration. For all other cycles, the Day 1 window is \pm 3 days.
- l) The period of safety observation extends from the time of consent until 30 days after the patient's last study treatment or until the AEs have resolved or stabilized or an outcome has been reached, whichever comes first.
- m) Concomitant medications should be collected beginning from within 4 weeks of Cycle 1, Day 1 until the end of the period of safety observation.
- n) In the event that a patient is unable to return to the clinic for a follow-up visit, telephone contact with the patient to assess AEs, concomitant medications, anti-cancer treatments will be conducted.

Appendix B. **SCHEDULE OF EVENTS OF COHORT A FOR Q3W DOSING (PART 2 AND 3)**

Activity	Screening	Cycles 1 and 2					Cycles 3-6 ^q	EOT ^l	30-day Follow-up, ^p
	≤28 days prior to 1st dose	Day 1^m	Day 2	Day 3	Day8 ±1 day	Day15 ±1 day	Day 1^m		(30-42 Days)
Informed Consent	•								
Demography	•								
Confirm disease diagnosis, stage at diagnosis and current stage	•								
Medical History	•								
Review and Document Inclusion/Exclusion Criteria	•								
Confirm patient continues to satisfy I/E Criteria		C1 only							
Physical examination ^a	•	•					•	•	•
Vital Signs ^b	•	•			•	•	•	•	•
Health-related Quality of Life ^c		•					•	•	•
Weight	•	•					•	•	•
Height	•								
B-symptoms	•	•					•	•	•
ECOG performance status	•	•					•	•	•
Pregnancy test (urine or serum)	•	•					•	•	•
Hematology and Chemistry ^d	•	•	•	•	•	•	•	•	•

Activity	Screening	Cycles 1 and 2					Cycles 3-6 ^q	EOT ^l	30-day Follow-up ^{g, p}
	≤28 days prior to 1st dose	Day 1^m	Day 2	Day 3	Day 8 ±1 day	Day 15 ±1 day	Day 1^m		(30-42 Days)
Coagulation ^d	•	•					•	•	•
Urinalysis ^d	•	•					•	•	•
Viral Serology (HBsAg)	•								
Radiologic tumor Assessments ^e	•		Every 6 weeks (\pm 1 week) from Cycle 1, Day 1 (no schedule shift due to dose delays) ^f					• ^g	• ^g
Biopsy tumor tissue ^h	•								
Bone Marrow Assessment ⁱ	•		Every 6 weeks (\pm 1 week) from Cycle 1, Day 1 as Clinically Indicated						
ECG (12-lead) ^k	•	•	•				•	•	•
Pharmacokinetic and Immunogenicity Assessments	See Appendix E								
AE and SAE evaluation ⁿ	•	•	•	•	•	•	•	•	•
Concomitant Medication ^o	•	•	•	•	•	•	•	•	•
Debio 1562 Infusion		•					•		
Rituximab Infusion		•					•		

a) Directed physical examination is acceptable while on study treatment and at the 30-day safety Follow-up Visit. Complete examination is required at screening and EOT. Physical examinations may be performed up to 3 days prior to study drug administration on Day 1 of all Cycles.

b) **Debio 1562** - vital signs (blood pressure, heart rate, temperature, and respiratory rate) will be measured immediately before each administration, every 30 min \pm 5 min during the infusion (if applicable), and immediately after infusion. **Rituximab** - vital signs will be measured immediately before each administration, every 60 min \pm 5 min during the infusion and immediately after infusion. Patients will remain in the clinic under monitoring for four hours after completion of the rituximab infusion for the first cycle. Post-administration safety monitoring could potentially be shortened (i.e. < 4 hours but at least 1 hour) following subsequent administration of rituximab, based on the judgement of the investigator. Patients receiving Debio 1562 only will also remain in the clinic under monitoring for one hour.

- c) HRQoL assessment at Day 1 of each cycle will be performed prior to Debio 1562 infusion.
- d) Laboratory assessments may be performed up to 3 days prior to study **drug** administration **in all cycles**. If the screening laboratory assessments are performed within 3 days prior drug administration on Day 1 of Cycle 1, no assessments need to be repeated on Day 1 of Cycle 1. All draws on Day 1 of treatment should be pre-dose. In the event of severe toxicity, repeat laboratory tests should be performed within 48 hours, and then followed at least twice weekly until retreatment criteria are met.

Serum Chemistry- ALB, ALK-P, ALT, AST, BUN, Ca, Cl, Creatinine, Glucose, LDH, Magnesium, Phosphorus, K, Na, Total bilirubin, Total protein, Uric acid, Immunoglobulin levels (IgG, IgA, IgM).

Hematology- Hct, Hgb, Platelet count, RBC count, WBC count with differential.

Urinalysis - Appearance, specific gravity and pH, Semi-quantitative dipstick evaluation of glucose, protein, bilirubin, ketones, leukocytes and blood, Microscopic examination of sediment to be performed if urinalysis is positive for WBC, proteins or blood.

Coagulation tests: T/INR and aPTT.

If deemed necessary by the Investigator an additional hematological assessment can be performed on Day 15 of Cycles 3-6.

- e) Radiographic tumor evaluation by CT or PET-CT scan of chest, neck, abdomen and pelvis will be performed within 28 days prior to first dose of study treatment. The anatomical regions to be assessed radiographically post baseline will be determined by individual patients' extent of disease. Whenever possible, the same radiographic scan assessment used at screening (e.g., PET-CT) should be used at all subsequent radiographic evaluations.
- f) Post-baseline disease assessments will be performed every 6 weeks from Cycle 1, Day 1 and will not shift due to dose delays.
- g) Patients discontinuing Debio 1562 for reasons other than PD will have subsequent clinic visits for radiographic assessment every 12 weeks (\pm 4 weeks) from the time of their last on-study tumor assessment until PD, or starting a subsequent anti-cancer therapy. For patients who discontinue for PD, no radiographic scans will be required at the EOT visit or the follow-up visits. All patients will be followed for survival every 12 weeks (\pm 4 weeks) from the time of the 30-day safety Follow-up visit, for up to one year from the last patient's first dose (Cycle 1 Day 1). Patients will not be required to visit the clinic for survival follow-up.
- h) Patients must have available a pathology-informed tumor biopsy sample representative of the current disease, [REDACTED].
- i) If applicable, a bone marrow biopsy or aspirate will be performed within 3 months prior to first dose. A repeat bone marrow biopsy or aspirate will be required for patients with bone marrow infiltration at baseline who have a CR by imaging and physical examination, and will, in case possible and deemed acceptable by the Investigator, be performed every 6 weeks as clinically indicated. In order to better understand the effect of Debio 1562 on WBCs, bone marrow biopsies/aspirates may also be requested for those patients who experience grade 4 cytopenias.

- [REDACTED]
- k) The screening ECG will be performed within 14 days prior to first treatment. In Cycles 1 and 2, ECGs will be performed within three hours prior to dose, at the end of the Debio 1562 infusion (to coincide with C_{max} and PK blood draw) and 24 ± 4 hours after infusion. An ECG will be performed on Day 1 of Cycles 3-6 to coincide with the pre-dose PK blood draw. An ECG at the 30-day Follow-up visit is not required unless clinically indicated or if the EOT assessment was missed.

- l) EOT visit should occur within 7 days of the decision to discontinue study treatment.
- m) Cycle 1 Day 1 assessments (ECOG, weight, B Symptoms and pregnancy test) do not need to be repeated if they are collected within 3 days of study drug administration. For all other cycles, the Day 1 window is ± 3 days.
- n) The period of safety observation extends from the time of consent until the 30 days after the patient's last study treatment or until the AEs have resolved or stabilized or an

outcome has been reached, whichever comes first.

- o) Concomitant medications should be collected beginning from 4 weeks prior to Cycle 1, Day until end of the period of safety observation.
- p) In the event that a patient is unable to return to the clinic for a follow-up visit, telephone contact with the patient to assess AEs, concomitant medications, and anti-cancer treatments will be conducted
- q) Permission to prolong the study treatment could be exceptionally granted by Study Sponsor if patients are deriving benefit from the study treatment and after complete presentation of the individual case by the Study Investigator, particularly the medical justification for extending the treatment and the re-assessment of the risk/benefit balance. The Sponsor's decision will consider the availability of IMP at the time of request. A report of the discussions with the Sponsor must be filed in the source documentation.

